9.1. Statistical Analysis Plan

The full statistical methods will be detailed in a Statistical Analysis Plan (SAP), which will be finalized prior to the first database lock.

9.2. Trial Design and Statistical Hypotheses

The primary endpoint is overall survival (OS). The primary hypothesis will be tested in the trial, aiming at claiming superior efficacy of the experimental Arm 1 (devimistat + mFFX) over the control Arm 2 (FFX) at the final analysis when the pre-specified number of deaths is reached. The trial is powered to detect an OS hazard ratio equal to 0.7 (a 30% reduction in the risk of death from any cause), assuming a median OS equal to 12 months in the control arm vs. 17.14 months in the experimental arm. Progression-free survival (PFS) will be tested if the primary endpoint reaches significance. Specifically, the hypotheses of interest is that PFS is equal to 6.4 months in the control arm vs. 9.14 months in the experimental arm, i.e. a PFS hazard ratio (HR) equal to 0.7 (a 30% reduction in the risk of tumor progression or death from any cause).

9.3. Analysis Populations

The following populations will be defined for the statistical analysis:

- The intent-to-treat (ITT) population includes all randomized subjects in the treatment arm they were allocated to
- The Per Protocol (PP) population consists of randomized subjects who do not have any major protocol violation and received at least one dose of study treatment
- The safety population consists of all subjects who received at least one dose of study treatment and have at least one post-baseline safety assessment

The ITT population will be used for all analyses of efficacy and baseline characteristics. The PP population will be used as a sensitivity analysis for efficacy endpoints. The safety population will be used for safety analyses.

Every effort will be made to keep all randomized patients in the study regardless of their adherence to treatment. Patients who stop their therapy for any reason will be followed until confirmed disease progression and/or death.

9.4. Description of Statistical Methods

9.4.1. General Analytical Considerations

One-sided tests will be used at a significance level equal to 0.025. Two-sided confidence intervals will be computed for a coverage of 0.95.

Time to event outcomes (“survival times”) will be described by treatment arm using the Kaplan-Meier method. Subjects who have not had the event of interest at the time of the analysis will be censored at the time of the last follow up. Summary statistics will be provided by treatment arm in terms of the number of events, median and 95% confidence interval, and survival probabilities at specific time points (such as 1 year, 2 years, etc.). Survival curves will be plotted by treatment arm and compared with a log-rank test stratified by performance status and tumor location. A stratified Cox regression model will be used to estimate the hazard ratio and its 95% CI, as well as to adjust the comparison for baseline covariates.

Binary outcomes will be described by proportions by treatment arm and compared with a Cochran-Mantel-Haenszel (CMH) test stratified by performance status and tumor location. A logistic regression model will be used to adjust the comparison for baseline covariates.

9.4.2. Testing Procedure and Control of Type I Error

This study has one primary efficacy endpoint of OS. The key secondary efficacy endpoint is PFS. Only one efficacy analysis is planned for all endpoints.

Testing of these two endpoints will proceed as follows in order to control the overall one-sided type I error of 0.025:

- OS will be tested at a significance level of 0.025. OS will be tested only once at the final analysis.
- PFS will be tested conditionally on the primary endpoint of OS reaching statistical significance, using the significance level of 0.025.

If OS reaches statistical significance and PFS also reaches statistical significance, then the hierarchical testing procedure will continue to test the other secondary endpoints in the following order: ORR first, and then DOR, each at a significance level of 0.025.

9.4.3. Efficacy Analysis

Patients will be allocated to either the control arm or the experimental arm using stochastic minimization, a dynamic treatment allocation procedure that produces good balance with respect to several prognostic factors between the randomized arms (Buyse, 2000)²⁰. When such a procedure is used, the preferred test is a re-randomization test (Simon, 1979)²¹ based on a large number of simulated trials in which patients are re-allocated randomly to the control arm or the experimental arm using the same stochastic minimization, so as to produce an empirical distribution of the test statistic under the null hypothesis. This empirical distribution is used to assign a statistical significance (a re-randomization *P*-value) to the observed test statistic. Arbitrary precision on the re-randomization *P*-value can be obtained by increasing the number of simulated trials. Full details on the re-randomization tests will be provided in the Statistical Analysis Plan. Re-randomization tests will be used as the primary method of analysis, with asymptotic tests used as sensitivity analyses.

The primary analysis will compare the OS observed under the combination therapy devimistat plus mFFX compared to standard care FFX in the ITT population. The comparison will use a re-randomization test based on the log-rank test-statistic, stratified by performance status (0 vs 1) and primary tumor location (head vs. body vs. tail of the pancreas). A stratified log-rank test will be performed as sensitivity analysis. Additional analyses with an unstratified log-rank test and re-randomization test with an unstratified log-rank test-statistic will also be performed. In addition, other sensitivity analyses will be performed, including the censoring of patients who changed treatment at the day the patient received the new treatment and performing all analyses described above on the PP population. The estimation of the survival curves for the 2 treatment groups will be generated using the Kaplan-Meier methodology. More details will be contained in the Statistical Analysis Plan (SAP).

PFS is defined as the duration from the date of randomization to the date of progressive disease or death from any cause. Patients who have neither progressed nor died will be censored at the day of their last radiographic tumor assessment, if available or date of randomization if no post initiation radiographic assessment is available. If death or PD occurs after 2 or more missing

radiographic visits, censoring will occur at the date of the last radiographic visit that the patient was known to be alive and progression-free. Patients who switch to another treatment prior to PD will be censored at the time of the treatment switch.

The primary analysis will compare the PFS observed under the combination therapy devimistat plus mFFX compared to standard care FFX based on the central assessment in the ITT population. The comparison will use a re-randomization test based on the log-rank test-statistic, stratified by performance status (0 vs 1) and primary tumor location (head vs. body vs. tail of the pancreas). A stratified log-rank test will be performed as sensitivity analysis. Additional analyses with an unstratified log-rank test and re-randomization test with an unstratified log-rank test-statistic will also be performed. The estimation of the survival curves for the 2 treatment groups will be generated using the Kaplan-Meier methodology. More details will be contained in the Statistical Analysis Plan (SAP).

The final analysis of PFS will include sensitivity analyses under the following conditions:

- Using central review PFS from the Per Protocol population
- Using the investigator provided PFS but censoring patients who changed treatment at the day the patient received the new treatment
- Using the Investigator provided PFS from the Per Protocol population

The SAP will further elaborate on other sensitivity analyses considering different censoring rules to control for missing data and/or lost to follow-up.

The secondary endpoint ORR will be estimated as the proportion of responders in each treatment arm of the ITT, defined as a patient whose best overall response is PR or better during the treatment period. All responses must be confirmed at least 4 weeks after the initial response is seen. The ORR analysis will compare the ORR per central assessment observed under the combination therapy devimistat plus mFFX compared to standard care FFX in the ITT population, considering patients without response assessment as non-responders. The comparison will use a re-randomization test based on the CMH test-statistic. The odds ratio and 95 % confidence interval of the odds ratio will be presented.

As a sensitivity analysis, a CMH test will be performed. In addition, both analyses (re-

randomization and CMH test) will be performed on the PP population.

The duration of response is the interval from date of initial documented response (CR or PR) to the first documented date of disease progression or death. Patients who do not relapse or die are censored at the day of their last tumor assessment. The DOR analysis will be a re-randomization test on the ITT population, based on the log-rank test-statistic. As a sensitivity analysis, a log-rank test will be performed. These analyses will only include responders.

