The patient's best response within the first 12 cycles of treatment as determined by the independent assessment will be used in the recording of the ORR for each patient. OS will be monitored every 2 months via telephone contact after treatment termination. (Note: During post-study treatment telephone contact, information related to cancer treatment received after the study will also be collected). OS will be calculated from the day of randomization. The duration of OS will be measured until the date of death or censored at follow-up. Patients who are lost to follow-up, withdraw from follow-up or alive and progression free will be censored at the date of last follow-up for OS.

Progression free survival (PFS) is calculated from the date of randomization to the date of progressive disease or death from any cause. Patients who have neither progressed nor died will be censored at the day of their last radiographic tumor assessment, if available, or date of randomization if no post initiation radiographic assessment is available. If death or PD occurs after 2 or more missing radiographic visits, censoring will occur at the date of the last radiographic visit that the patient was known to be alive and progression-free.

Duration of response is calculated from the date of randomization to the date of confirmed clinical/radiological progression or death from any cause.

Biological Specimen Collection and Laboratory Evaluations:

Up to 10 unstained slides will be submitted when available from the pre-study diagnostic biopsy and the study's progression of disease biopsy (if available).

Blood Sampling for Pharmacokinetic (PK) Analysis:

PK sampling will occur only for the study Arm 1: devimistat + mFFX because the dosing level of Oxaliplatin and Irinotecan between mFFX (in Arm 1) and FFX (in Arm 2) are different. As such, PK comparison of components between mFFX and FFX is not appropriate and therefore no PK sampling for the study Arm 2: FFX.

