5.4 Control Of Type I Error

This study has one primary endpoint of OS. The key secondary efficacy endpoint is PFS.

Testing of these two endpoints will proceed as follows in order to control the overall one-sided type I error of 0.025:

- OS will be tested at a significance level of 0.025. OS will be tested only once at the final analysis.
- PFS will be tested conditionally on the primary endpoint of OS reaching statistical significance, using the significance level of 0.025.
- If OS reaches statistical significance and PFS also reaches statistical significance, then the hierarchical testing procedure will continue to test the rest of the other secondary endpoints in the following order: ORR first, and then DOR, each at a significance level of 0.025.

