Supplementing this test will be a Kaplan-Meier plot showing time to progression or death from randomization, in months, by treatment arm. Underneath the plot should be a table displaying the number at risk by treatment arm at 0.5-month intervals. The plot should contain an inset with the hazard ratio, the corresponding confidence limits and p-values (both asymptotic and re-randomization test p-values).

Refer to the table below for a description of the primary and sensitivity analyses that will be performed.

No.	Stratified	Re-Randomized	Endpoint Review	Population	Additional Censoring
1. Primary	Yes	Yes	Central	ITT	2 missed visits: Y; New therapy: Y
1. Sensitivity	Yes	No	Central	ITT	2 missed visits: Y; New therapy: Y

Confidential

2. Sensitivity	Yes	No	Central	ITT	2 missed visits: N; New therapy: Y
3. Sensitivity	Yes	No	Central	PP	2 missed visits: Y; New therapy: Y
4. Sensitivity	Yes	No	Investigator	ITT	2 missed visits: Y; New therapy: Y
5. Sensitivity	Yes	No	Investigator	PP	2 missed visits: Y; New therapy: Y

The estimand corresponding to this secondary endpoint is defined by the following 5 attributes:

TREATMENT

Combination CPI-613 + mFFX compared to standard of care FFX

POPULATION

Population of patients with metastatic adenocarcinoma of the pancreas, defined through inclusion/exclusion criteria to reflect the target population. Analysis will include all randomized patients (ITT population).

VARIABLE

Progression-free survival, calculated as time from date of randomization to the date of progressive disease (assessed by an independent, blinded, central review) or death from any cause.

INTERCURRENT EVENTS (ICE) AND STRATEGIES

Death occurring before progression is observed/documented: composite strategy

Death will be considered as an event as per PFS definition.

Events leading to 2 or more consecutive missed radiographic scans before progression or death is observed: while-on-treatment strategy

radiological assessments before observed progression will be censored on the last radiological scan with documented non-progression.

Covid-19 pandemic related intercurrent events (other than those falling in the above categories): treatment policy

Treatment effect will be evaluated regardless of impact of the pandemic situation.

Treatment discontinuation: treatment policy

Any early discontinuation of treatment will be ignored (ITT principle).

Initiation of new anti-cancer therapy: hypothetical strategy

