6.3.2 DOR

Duration of response is defined as the time from the date of first documented response until date of documented progression or death in the absence of disease progression (i.e. date of PFS event or censoring – date of first response + 1). The end of response should coincide with the date of progression or death from any cause used for the PFS endpoint. The time of the initial response will be defined as the first date of the dates contributing towards the first visit response of PR or CR. If a patient does not progress following a response, then their DoR will use the PFS censoring time. DoR will not be defined for those patients who do not have documented response.

To assess for DOR differences between treatment arms, the Cox PH model will be used, specifying the Efron method for ties. This will be done using `PROC PHREG` in SAS, in which performance status and tumor location will be added in a separate `strata` statement.

The significance of the asymptotically estimated statistics will be determined using a re-randomization procedure. The hazard ratio, and confidence limits from the asymptotic test, will be reported.

The Kaplan-Meier estimator, and their respective confidence limits, will all be displayed in a table. To confirm proportionality of the hazards, the log-log survival plot should be inspected, using `PROC LIFETEST` and, at a minimum, specifying treatment arm in the `strata` statement (the stratification variables may also be included); these plots will not be included in the set of outputs.

Supplementing this test will be a Kaplan-Meier plot showing DOR duration, in months, by treatment arm. Underneath the plot should be a table displaying the number at risk by treatment arm at 0.5-month intervals. The plot should contain an inset with the hazard ratio, the corresponding confidence limits.

A log rank test will be performed as a sensitivity analysis.

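### The last confirmatory test compares duration of response among responders only, so its 0.025 level does not hold for a treatment effect on duration

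*Protocol*

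**What the plan says.** Protocol 9.4.2 sets up sequential testing of OS and then PFS to "control the overall one-sided type I error of 0.025". If both are significant, testing goes on with "ORR first, and then DOR, each at a significance level of 0.025". SAP 5.4 has the same order and level: the procedure will "continue to test the rest of the other secondary endpoints in the following order", ORR before DOR.

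The DOR paragraph of Protocol 9.4.3 states "The DOR analysis will be a re-randomization test on the ITT population", and then "These analyses will only include responders". SAP 6.3.2 agrees on who is analysed: "DoR will not be defined for those patients who do not have documented response". The p-value comes from the re-randomisation procedure of SAP 6.1. SAP 3.1.2 frames the objective as DOR on CPI-613 plus mFFX versus FFX.

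The SAP gives OS a five-attribute estimand (6.2.1) and does the same for PFS (6.3.1: "The estimand corresponding to this secondary endpoint is defined by the following 5 attributes"). It gives none for DOR, and neither document labels the DOR comparison descriptive.

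The start date also differs. Protocol 7.1.1 says "Duration of response is calculated from the date of randomization", whereas Protocol 9.4.3, SAP 5.6 and SAP 6.3.2 start the clock at first response.

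**The concern.** Randomisation makes the arms comparable as randomised. It does not make the responders in one arm comparable with the responders in the other once treatment affects who responds. In this sequence DOR is tested only after ORR has been found to differ, so the comparison is made exactly when the trial has concluded that treatment changes membership of the compared groups. The arms also differ in oxaliplatin and irinotecan dose (Tables 7 and 8), so the experimental arm could lose some responders as well as gain others.

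If the added responders tend to have long durations, DOR will look better on the experimental arm even though no patient's duration has changed. If they tend to have short ones, the test leans towards control and can hide or reverse a real benefit. Either way, a formally significant DOR would stand beside OS, PFS and ORR as a confirmatory result. The bias cannot be removed afterwards from the responder data, because its size and sign depend on a link between response and duration that the trial does not identify.

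**Working it through.** **The plan's own figures.** At HR 0.7, 90% power and one-sided 0.025:

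- Schoenfeld: 4(1.960 + 1.282)² / (ln 0.7)² = 42.04 / 0.1272, which rounds up to 331.
- Freedman: (1.960 + 1.282)² × (1.7 / 0.3)² = 10.51 × 32.11, which rounds up to 338.

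The stated 335 deaths and 330 PFS events reproduce. The documents give no power calculation for DOR; the figure at issue is its 0.025 level.

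**How far the responder sets can differ.** Inputs are 250 per arm (Protocol 9.5, 1:1), control ORR 31.6% and phase I ORR 61% (Protocol 2.1.5.2.1). An experimental ORR of 45% is an assumption. Suppose nobody loses a response:

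- Control responders: 0.316 × 250 = 79.
- ORR 45%: 0.45 × 250 = 112.5, so 33.5 / 112.5 = 30% of experimental responders have no counterpart among control responders.
- ORR 61%: 0.61 × 250 = 152.5, so 73.5 / 152.5 = 48%.

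**Simulation 1.** Each patient has one response duration, the same under either arm, so any DOR difference is false. Further inputs from the documents are median DOR 5.9 months, accrual over 33 months and analysis at the 335th death. Assumed are response at 2 months, exponential durations, and non-responder PFS and post-progression survival giving OS HR 0.62 to 0.74 and PFS HR 0.68 to 0.77. There were 4,000 trials per scenario; OS, PFS and ORR were all significant in 68% to 86%. Among those trials, by the assumed latent correlation between response and duration:

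| DOR falsely favours | ORR | −0.6 | −0.3 | 0 | +0.3 | +0.6 |
|---|---|---|---|---|---|---|
| Experimental | 45% | 20% | 7.6% | 3.2% | 0.9% | 0.1% |
| Experimental | 61% | 71% | 21% | 3.7% | 0.4% | 0% |
| Control | 45% | 0.1% | 0.5% | 1.3% | 3.8% | 10% |
| Control | 61% | 0% | 0% | 0.6% | 7.6% | 42% |

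The joint probability of passing the first three tests and then falsely favouring the experimental arm is 0.17 (ORR 45%) and 0.60 (ORR 61%) at −0.6, and 0.027 and 0.030 at 0. With equal ORR and no preceding tests, the false-favourable rate is 2.5% to 2.8% at every correlation. The inflation therefore comes from the difference in who responds.

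**Simulation 2, a different model.** Patients respond on both arms, on one arm only, or on neither, and nobody's duration changes. Settings: exponential durations, censoring uniform over 3 to 30 months (assumed), unstratified log-rank test, 8,000 trials per scenario, no OS or PFS condition. Rejection rate in favour of the experimental arm:

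| Median DOR of added responders relative to control responders | ORR 45% | ORR 61% |
|---|---|---|
| Half | 0.001 | 0.000 |
| Equal | 0.032 | not run |
| 1.5 times | 0.11 | 0.25 |
| Twice | 0.235 | 0.54 |

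If the experimental arm loses 10 points of short-lived responses and gains 23.4 points of ordinary ones (31.6 − 10 + 23.4 = 45%), the rate is 0.23. With no effect on response or duration it is 0.028.

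**Does re-randomisation help?** SAP 6.1 re-allocates arms and keeps each patient's observed outcome, including response status. That is valid under the null that treatment affects neither response nor duration, but the ORR test has just rejected its first half. In the first model with only the ORR condition (1,500 trials, 999 simple equal-arm re-allocations rather than the minimisation algorithm), the rates at −0.6, 0 and +0.6 were 0.197, 0.030 and 0.002 for ORR 45%. The ordinary log-rank test gave 0.200, 0.031 and 0.001.

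**The case against.** The strongest reply is that DOR is openly defined as a responder endpoint. Its natural null is equal DOR among observed responders, and for that null the test is about nominal. This is correct, but that null is not a treatment effect, while the stated objective is a comparison versus FFX. With no DOR estimand, the SAP does not say which null is meant. ORR has no five-attribute estimand either, but its analysis keeps every ITT patient in the denominator.

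Second, the stated overall error control refers to OS and PFS, and DOR is last and gives alpha to nothing. This stands, and it limits the damage to the DOR claim itself. The plan still assigns DOR a confirmatory 0.025.

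Third, the large false-favourable rates need a negative link between response and duration, and nothing in the documents supports one. Under a latent normal model, −0.6 implies added responders lasting about 1.9 to 2.2 times as long as control responders, which is strong. The 61% is 11 of 18 evaluable phase I patients by investigator assessment, whereas this trial uses confirmed, centrally read responses. Both points stand, so the upper figures are illustrations and not forecasts. A positive link makes false claims for the experimental arm rarer than 2.5%, but it then biases the test towards control, so the stated level fails in either direction.

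Fourth, conditional rates look worse than joint ones. Both are shown above; at −0.6 the difference is modest.

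Finally, calling the population ITT can be read as responders within ITT as opposed to per-protocol. That is a fair reading, and only the wording needs correcting.

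**Conclusion.** The concern holds. The DOR step does not guarantee one-sided 0.025 for the hypothesis that treatment changes no patient's response duration, and a significant DOR cannot be read as an effect on duration. This follows from the design: a comparison restricted on an outcome observed after randomisation, made after that outcome has been shown to differ.

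The size is illustrative. Across the assumed links, the false-favourable rate in trials that reach the step runs from 0.1% to 20% at ORR 45% and from 0% to 71% at ORR 61%. It is near nominal (3.2% and 3.7%) only when response and duration are unrelated. These rates rest on exponential durations, an assumed response–duration link, an assumed ORR of 45% or the phase I 61%, and simplified allocation.

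The change should be made, but the primary conclusion is not at risk: error control for OS, PFS and ORR is intact.

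**What to change.** - In Protocol 9.4.2 and SAP 5.4, end the alpha-controlled sequence at ORR.
- In Protocol 9.4.3 and SAP 6.3.2, report DOR by arm descriptively with the Kaplan-Meier estimates and confidence limits already planned, labelled as a non-randomised comparison among responders. Remove the formal test.
- If a between-arm comparison is wanted, use time in response in all ITT patients, with non-responders counted as zero, and write out its estimand. This measure combines response rate and duration, so it must not be presented as an effect on duration alone.
- Replace the ITT label in the DOR paragraph of Protocol 9.4.3 with responders within the ITT population.
- Separately, align the DOR start date in Protocol 7.1.1 with Protocol 9.4.3, SAP 5.6 and SAP 6.3.2. This is a distinct inconsistency, but it affects the same endpoint.

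The cost is wording in two documents and the loss of one formal p-value at the end of the sequence. No new data are needed.
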